UTI	Urinary Tract Infection

AMENDMENT HISTORY

Amendment No.	Protocol Version	Date	Details of Changes made
EC Submission	1.16	25-May-2020	-
Supplemental EC submission	1.17	17-Jul-2020	Data analysis was changed
1	1.18	04-Nov-2020	Study Sites were added
2	1.19	09-Aug -2021	Clarification of inclusion criterion 2 eCRF (HybridForms®) Time schedule
3	1.20	22-Dec-2021	Study site (Uniklinikum St. Pölten) was added Additional Information about SAE Reporting Timeframe correction of secondary outcomes

confidential

Synopsis

Sponsor	Medical University of Graz [name] [name], Austria
Coordinating Investigator	[name], MD, Associate Professor
Indication	Patients with HFrEF or HFmrEF, and ICD±CRT therapy
Study design and phase	Randomized, prospective, placebo-controlled, double blind, multicenter, phase III study in patients with HFrEF or HFmrEF, and ICD±CRT therapy
Study Short Title	Ertugliflozin to Reduce Arrhythmic burden in ICD/CRT patientS
Keyword	SGLT-2 inhibition, heart failure, ICD, CRT, VT
Aims of the trial	The primary objective is to investigate the impact of Ertugliflozin on total burden of ventricular arrhythmias. Further objectives will be number of therapeutic interventions of implanted devices, atrial fibrillation, heart failure biomarker and changes in physical function quality of life, stress and anxiety.
Outcome measures of the trial	
Primary outcome measures:
 
Difference in number of sVT/VF episodes between treatment groups from randomization to week 52
 
Secondary outcomes measures:
 
Difference in nsVT episodes between treatment groups from randomization to week 52
 
Difference in number of appropriate therapeutic ICD therapies between treatment groups from randomization to week 52
 
Difference in the change of nt-proBNP levels between treatment groups from randomization to week 52
 
Difference in the change of HbA1c between treatment groups from randomization to week 52 (in subjects with known T2DM)
 
Difference in the number of hospital re-admissions due to heart failure between the treatment groups from randomization to week 56
 
Difference in the duration of hospital stay between the treatment groups after initiation of the study treatment from randomization to week 56
 
Difference in cardiovascular mortality between treatment groups from randomization to week 56

Number of patients	402 patients
Time schedule	
With reference to the trial:
 
EC Submission: NOV/2020
 
Local Authority Submission: SEP/2020
 
First Patient First Visit (FPFV): JUN/2021

Last Patient First Visit (LPFV): JAN/2023

Last Patient Last Visit (LPLV): JAN/2024

Data Base Lock: APR/2024

First Results available: JUN/2024

Clinical Study Report: JUN/2024

With reference to patients:

Duration of the treatment: 12 months

Main inclusion criteria

- 1) HFrEF or HFmrEF, and ICD±CRT therapy > 3 months
- 2) At least 10 documented VT episodes (either nsVT or sVT ± ICD treatment) within the last 12 months plus:
 - nt-proBNP > 500pg/mL or
 - LV-EF < 35% or
 - hospitalization for heart failure within the last 12 months or
 - >100nsVTs within the last 12 months
 - >1 sVT/VF within the last 12 months
- 3) Informed consent has to be given in written form.
- 4) eGFR > 30 ml/min/1.73m²
- 5) Blood pressure before first drug dosing: RR_{systolic} >100mmHg
- 6) Blood pressure before first drug dosing: RR_{diastolic} >60mmHg
- 7) 18 – 80 years of age

Main exclusion criteria

- 1) Any other form of diabetes mellitus than type 2 diabetes mellitus, history of diabetic ketoacidosis
- 2) Ongoing ventricular arrhythmia
- 3) Known allergy to SGLT-2 inhibitors
- 4) Haemodynamic instability as defined by intravenous administration of catecholamine, calciumsensitizers or phosphodiesterase inhibitors
- 5) >1 episode of severe hypoglycaemia within the last 6 months under treatment with insulin or sulfonylurea
- 6) Planned catheter ablation for ventricular arrhythmia
- 7) Planned explantation of ICD, or planned up/downgrade to/from CRT-D device

Study medication

Active substance: Ertugliflozin

Commercial name: Steglatro

Manufacturer: MSD

Treatment plan

Ertugliflozin, 5mg once daily orally administered or matched placebo

1. INTRODUCTION AND RATIONALE

Sodium-dependent glucose cotransporter 2 (SGLT2) is mainly expressed in human kidneys and small intestinal cells. In the proximal tubule of the nephron SGLT2 is responsible for the reabsorption of approximately 90% of the filtrated glucose. Inhibition of SGLT2 was shown to increase renal glucose excretion and to lower glucose. Subsequently, a number of SGLT-2 inhibitors were developed and are currently approved for the treatment of type 2 diabetes. CV outcome trials, required by the European Medicines Agency (EMA) and Federal Drug Administration (FDA) have proven additional beneficial effects on cardiovascular outcome in various compounds of that class. Empagliflozin could even show significant positive effects on mortality(1). More consistent and most pronounced was the effect of reducing heart failure hospitalisation. Most recently, data of dapagliflozin was published (DAPA-HF)(2) extending these beneficial effects to non-diabetic heart failure patients, significantly reducing the primary endpoint of CV death and worsening heart failure as well as CV-mortality alone and even all course mortality.

As dose-response modelling indicates that ertugliflozin 5 mg and 15 mg result in near maximal urinary glucose excretion (UGE) in patients with type 2 diabetes mellitus, providing 87% and 96% of maximal inhibition, respectively (product information Steglatro), the lower dose can be expected to be comparably efficient and will therefore be used in this study. This is also confirmed by the data of a recent pooled analysis of previous phase III trials with ertugliflozin showing a reduction in HbA1c of only 0.1% (3).

Ventricular arrhythmias are a typical feature of advanced heart failure with reduced ejection fraction (HFrEF) or heart failure with mid-range ejection fraction (HFmrEF), and account for a large proportion of cardiac death in this population. Implantation of an ICD is a class IA recommendation in the ESC heart failure guidelines both in secondary prevention and primary prevention (IB for DCM patients)(4). Additional CRT function is a class IA recommendation in all of these patients with QRS duration >150ms in sinus rhythm(4). Since arrhythmias occur independent of the type of cardiomyopathy (ischemic, dilative, idiopathic) the unifying phenotype of altered contractility and elevated diastolic pressure and potentially increased systemic inflammation itself must be regarded as the trigger of these arrhythmias(5).

Therefore, every improvement of heart failure should result in a reduction of ventricular arrhythmias. This has been shown extensively for beta-blockers(6), aldosterone-antagonists(7; 8), and ARNIs(9; 10). Large outcome studies with ACE inhibitors did only give limited insight in the type of arrhythmic events, their causes, and the effect of the treatments(11; 12), while studies analysing the rate of ventricular arrhythmias did show a significant reduction in these events(13).

Previous data showed that SGLT-2 inhibitor dapagliflozin (DAPA-HF) improved primary outcome in a HFrEF population comparable to sacubitril/valsartan in the PARADIGM trial(9) (both trials with a NNT of 21). Therefore, a comparable impact on heart failure morbidity and ventricular arrhythmias can be assumed for both drugs. Moreover, Martens et al. reported on a highly significant reduction of ventricular arrhythmias after initiation of sacubitril/valsartan in a retrospective analysis of 151 patients with an observation period of 6 months. The number of VT/VF episodes declined by more than two thirds(10).

Mortality in patients on ICD therapy is high despite optimal medical treatment. The study by Martens is a retrospective analysis of data of patients that were followed throughout the observation period of 364 days.

Therefore, severely ill patients and at least those who died within these 12 months were not analysed. Obviously, these patients tend to have the highest burden of ventricular arrhythmias. Therefore, event rate in the Martens study is underestimated.

More reliable data on event rates derive from prospective randomized trials such as the RAFT study. They report a rate of VTs of ~2 per year (11278 appropriate ICD detections in 5953.6 patient-years of follow-up) in a cohort of patients with severely reduced left ventricular ejection fraction (<30%).

Within another increased-risk population treated in the SHIELD trial 58% of the placebo-group experienced “all-cause shocks plus symptomatic tachyarrhythmias terminated by ATP”. The overall number of episodes was 1595 in 214 patients (average of ~7.5/patient and year).

1.1 Aim of the study

The aim of this mechanistic study is to investigate the impact of ertugliflozin on the ventricular arrhythmic burden, physical function, quality of life and biomarkers in heart failure in patients with ICD±CRT therapy.

1.2 Study hypothesis

Treatment with the SGLT-2 inhibitor ertugliflozin will reduce sVT/VF episodes more effectively than placebo within 12 months.

2. OBJECTIVES AND OUTCOMES

2.1 Primary and Secondary Objectives

The primary objective is to investigate the impact of ertugliflozin on ventricular arrhythmia burden. Further objectives will be the number of therapeutic interventions of implanted devices, atrial fibrillation, heart failure biomarker and changes in physical function, quality of life, stress and anxiety.

2.2 Safety objectives

- All-cause mortality
- Number of serious adverse events
- Number of hypoglycaemic events
- Number of genital infections
- Number of ketoacidotic events
- Number of ventricular electric storm episodes
- Changes in liver function parameters (AST, ALT, GGT)
- Changes in renal function parameters (creatinine, eGFR)

2.3 Primary outcome

Difference in number of sVT/VF episodes between treatment groups from randomization to week 52

2.4 Secondary outcomes

Secondary outcomes measures:

Difference in nsVT episodes between treatment groups from randomization to week 52

Difference in number of appropriate therapeutic ICD therapies between groups from randomization to week 52

Difference in the change of nt-proBNP levels between treatment groups from randomization to week 52

Difference in the change of HbA1c between treatment groups from randomization to week 52 (in subjects with known T2DM)

Difference in the number of hospital re-admissions due to heart failure between the treatment groups from randomization to week 56

Difference in the duration of hospital stay between the treatment groups after initiation of the study treatment from randomization to week 56

Difference in cardiovascular mortality between treatment groups from randomization to week 56

3. STUDY DESCRIPTION

3.1 Design

This is a randomized, double-blind (patients and physicians), placebo controlled multi-center study to evaluate the effect of ertugliflozin 5mg once daily (p.o.) for 52 weeks on the ventricular arrhythmic burden and markers of physical and mental well-being as well as biomarker for heart failure in HFrEF and HFmrEF patients with ICD±CRT therapy. The study will be conducted in 8 experienced sites in Austria with an aim to enrol 402 patients (Figure 1) to evaluate the overall study hypothesis.

[figure not shown]

Figure 1 Study Flow Chart

3.2 Duration of study

It is anticipated that the study will run for 30 months.

4. STUDY POPULATION

We will study subjects with HFrEF or HFmrEF and ICD±CRT therapy with ≥ 10 episode of non-sustained VT within the last 12 months before enrolment. We aim to recruit $>30\%$ of subjects with established type 2 diabetes mellitus.

4.1 Inclusion criteria

- 1) HFrEF or HFmrEF and ICD±CRT therapy > 3 months
- 2) At least 10 documented VT episodes (either nsVT or sVT \pm ICD treatment) within the last 12 months plus
 - nt-proBNP $> 500\text{pg/mL}$ or
 - LV-EF $< 35\%$ or
 - hospitalization for heart failure within the last 12 months or
 - $>100\text{nsVTs}$ within the last 12 months- $> 1\text{sVT/VF}$ within the last 12 months
- 3) Informed consent has to be given in written form.
- 4) eGFR $> 30\text{ ml/min}/1.73\text{m}^2$
- 5) Blood pressure before first drug dosing: RR_{systolic} $>100\text{mmHg}$
- 6) Blood pressure before first drug dosing: RR_{diastolic} $>60\text{mmHg}$
- 7) 18 – 80 years of age

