5.5.2 ECG, echocardiography, ICD interrogation

An ECG, echocardiography, and ICD interrogation will be performed at the screening visit. In our study, ICDs are interrogated both with telemedicine (home-monitoring) and during on-site ICD follow-ups.

Patients will be offered to be included in our home-monitoring program. Currently, already 80% of patients have a home-monitoring device and routinely (every 4 months) transmit their data. In case of an alarm (sustained VT/VF) the data is transmitted automatically. In addition, all patients, regardless if they have a home-monitoring device or not, will be checked in the outpatient clinic on a yearly basis.

All arrhythmic events are recorded in the patient database. For this study, the number of episodes recorded during the study period will be tallied up.

All tests will be interpreted, signed and dated by the investigator before randomisation.

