Out of the > 1000 patients with ICD±CRT being seen at our out-patients clinic >50% have experienced episodes of non-sustained VT within the last 12 months. In order to enrich the study population with higher risk patients at least one additional inclusion criterion has to be met (either nt-proBNP > 500pg/mL or LV-EF < 35% or hospitalization for heart failure within the last 12 months or >100nsVTs or >1sVT/VF episode within the last 12 months).

About 5-10% of our patients are currently treated with ARNI. Expecting similar numbers in the other participating centers we feel confident to recruit patients for this trial within 18 months. Moreover, the recent DAPA-HF trial with 11% of patients on ARNI therapy revealed an unaltered benefit of SGLT-2 inhibition in these patients(2).

Taking into account that compared to the Martens-trial the expected reduction in the applied study is much lower, the observation period twice as long and the populations risk is enriched due to the inclusion criteria the calculation can be rated conservative.

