7.2 Data analysis

Intention-to-treat (ITT) analyses will be applied as the primary analysis. Analysis of the primary endpoint is comparison of the number of sVT/VF episodes between treatment groups from randomization to week 52. The primary endpoint will be analysed using analysis of covariance (ANCOVA), with treatment as a fixed factor, the baseline number of sVT/VF episodes as a covariate and with adjustment for history of T2D and eGFR and site of randomization.

Normally distributed variables will be presented as mean \pm standard deviation (SD) and skewed distributed variables as median and interquartile range [IQR]. Comparisons between treatment and placebo group will be performed by an unpaired two sample *t*-test, Mann–Whitney test, or χ^2 test as appropriate.

A two-tailed p-value ≤ 0.05 will be considered statistically significant. A detailed statistical analysis plan including pre-specified subgroup analyses will be finalized ahead of database lock.

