#### **3.2 Inclusion-Exclusion Criteria and General Study Population**

##### **3.2.1 Inclusion criteria**

- 1) HFrEF or HFmrEF and ICD±CRT therapy > 3 months
- 2) At least 10 documented non-sustained VTs within the last 12 months plus
  - nt-proBNP > 500pg/mL or
  - LV-EF < 35% or
  - hospitalization for heart failure within the last 12 months or
  - >100nsVTs within the last 12 months
- 3) Informed consent has to be given in written form.
- 4) eGFR > 30 ml/min/1.73m^2
- 5) Blood pressure before first drug dosing: RRsystolic > 100mmHg
- 6) Blood pressure before first drug dosing: RRdiastolic > 60mmHg
- 7) 18 – 80 years of age

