## **Ertugliflozin to Reduce Arrhythmic burden in ICD/CRT patientS (ERASe-Trial) – a phase III Study**

**RR =  $e^{\beta_1}$ .** The efficacy of the drug, compared to placebo, will then be investigated by testing the following null and alternative hypotheses:

$$H_0: \beta_1 = 0 \quad \text{vs.} \quad H_A: \beta_1 \neq 0$$

The function `glm.nb` from the MASS package in R will be used for this reason and for fitting the negative binomial regression model. The model will also adjust for the baseline number of sVT/VF. Sensitivity analysis will be carried out by using methods robust to outliers.

The analysis of secondary endpoints will be as follows: The number of incident nsVT, the number of appropriate ICD-treatment episodes, the total number of hospitalization due to heart failure will be analysed using a beta binomial model. The change in NTproBNP and the change in HbA1c levels from randomization to week 52 will be analysed using a multiple linear regression model. Hospitalization days from randomization to week 52 will be compared between the two groups using mean and SD. Cardiovascular mortality will be analysed by comparing proportions across the two groups.

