### **5.1 Covariates and subgroups**

All analyses, including the primary analysis, will be adjusted for the variables used when stratifying the randomization if the sample size permits. Analysis may also be adjusted for baseline levels of the dependent variables if available. No subgroup analyses are planned.

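### Baseline non-sustained VT burden, already counted to check eligibility, is not used in the primary sVT/VF model: an inexpensive efficiency gain of unknown size, not an error or a bias

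*Protocol*

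**What the plan says.** **Entry.** Protocol section 4.1, criterion 2, requires "At least 10 documented VT episodes (either nsVT or sVT", with or without ICD treatment, in the previous 12 months, plus a further risk criterion. Section 4 of the protocol describes the population by ten or more, in its words, "episode of non-sustained VT within the last 12 months before enrolment". SAP section 3.2.1 has "At least 10 documented non-sustained VTs within the last 12 months plus". None of the three requires a sustained event.

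**Risk marking.** Protocol section 7.1 states the purpose of the further criterion: "In order to enrich the study population with higher risk patients at least one additional inclusion criterion has to be met". It lists five alternatives, among them more than 100 nsVTs and more than one sVT/VF episode. The list in SAP section 3.2.1 has four and omits the sVT/VF one.

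**Primary model.** SAP section 5 specifies negative binomial regression and adds: "The model will also adjust for the baseline number of sVT/VF". Protocol section 7.2 has a different model (ANCOVA) but the same arrhythmia covariate, "the baseline number of sVT/VF episodes as a covariate", together with T2D history, eGFR and site. SAP section 5.1 adjusts all analyses for the stratification factors (site, type 2 diabetes, eGFR) if the sample size permits, and continues: "Analysis may also be adjusted for baseline levels of the dependent variables if available". Under that rule baseline nsVT may enter the nsVT secondary analysis but has no route into the primary one.

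**Data.** ICD interrogation takes place at visit 1 (protocol section 5.3), and section 5.5.2 says "All arrhythmic events are recorded in the patient database".

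**The concern.** The plan selects patients on a variable that it regards as a risk marker, then leaves that variable out of the model for the outcome. Because entry needs no sustained event, some patients will have a baseline sVT/VF count of zero, and the one arrhythmia covariate cannot tell those patients apart. Their nsVT counts can run from about 10 to over 100.

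What is at stake is precision only. SAP section 7 says that the trial ended early with a lower sample size, so precision can no longer be bought with more patients. It has to come from baseline data already collected.

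**Working it through.** **1. The plan's own figure.** SAP section 4 gives 191 per arm for control rate r0 = 1.3 per year, RR = 0.70 (r1 = 0.91), dispersion k = 1, follow-up t = 11.4/12 = 0.95 years and 80% power. The alpha is printed as 0.05% and is read here as 0.05.

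n = (z_α√V0 + z_β√V1)² / (ln RR)², where
- V1 = (1/r0 + 1/r1)/t + 2k = (0.769 + 1.099)/0.95 + 2 = 3.966
- V0 = 2/(t × 1.105) + 2k = 1.905 + 2 = 3.905, with 1.105 the mean of the two rates
- (ln 0.70)² = 0.1272

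With one-sided z_α = 1.645: (1.645 × 1.976 + 0.842 × 1.992)²/0.1272 = 190.8, hence 191; 382/0.95 = 402. With two-sided z_α = 1.960 the same inputs give 242.1, hence 243. So 191 matches a one-sided 5% test, whereas protocol section 7.2 is two-sided. That is a separate matter. Here 191 per arm serves only as the base case.

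**2. What the documents do not supply.** No section gives the correlation (ρ) between log nsVT burden and a patient's log sVT/VF rate. It is assumed and varied.

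**3. Simulation A: stable patient risk.** Inputs: 191 per arm, r0 = 1.3, RR = 0.70, t = 0.95, log-normal patient effects with squared coefficient of variation 1, the same patient effect at baseline and on study, about 250 runs per row. Negative binomial fits; power = Φ(0.3567/SE − 1.96).

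With treatment only, the SE of the log rate ratio is about 0.137 and the fitted k about 0.81. Adding log baseline sVT/VF lowers these to about 0.122 and 0.35. Adding nsVT on top:

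| ρ | SE, sVT/VF only | SE, plus nsVT | Variance ratio | Two-sided power |
|---|---|---|---|---|
| 0 | 0.1221 | 0.1222 | 1.001 | 83.2% → 83.1% |
| 0.3 | 0.1227 | 0.1221 | 0.990 | 82.8% → 83.2% |
| 0.5 | 0.1218 | 0.1196 | 0.965 | 83.4% → 84.7% |
| 0.7 | 0.1226 | 0.1175 | 0.919 | 82.9% → 85.9% |
| 0.8 | 0.1228 | 0.1144 | 0.868 | 82.7% → 87.6% |

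For example, at ρ = 0.7, (0.1175/0.1226)² = 0.919, a cut of 8%. Entering baseline sVT/VF untransformed gives ratios of 1.005, 0.986, 0.959, 0.908 and 0.877.

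**4. Simulation B: risk that drifts, more zeros at baseline.** Simulation A favours the SAP model, because the baseline sVT/VF count is then a nearly ideal proxy for on-study risk. With an assumed year-to-year correlation of 0.6–0.8, a baseline sVT/VF rate of 0.4–1.3 per year (about 40–76% of patients at zero) and k = 1 or 4, adding log nsVT to log(sVT/VF + 1) cuts the variance by about 1–3% (ρ = 0.3), 4–8% (ρ = 0.5) or 10–19% (ρ = 0.7). A mid-range case (correlation 0.7, baseline rate 0.8, k = 1) gives 2%, 6% and 13%.

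**5. Downside.** At ρ = 0 the variance rose by at most 0.5%. Under RR = 1, with 1,000 runs each, the rejection rates of the two models were 6.6% and 6.9% at 191 per arm, and 5.5% and 6.2% at 40 per arm. With a log link, randomised treatment and a common effect, a further baseline covariate leaves the rate ratio being estimated unchanged.

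**6. A small trial.** The documents do not give the final number of patients. At an assumed 40 per arm, power moved from 24.5% to 26.1%, 26.5% and 28.2% at ρ = 0.3, 0.5 and 0.7.

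**The case against.** The strongest objection is that the benefit is conjectural. Calling more than 100 nsVTs a mark of higher risk, as one of five alternatives, does not say how well the count predicts sVT/VF, still less what it adds once baseline sVT/VF is in the model. A reader might infer that precision is lost as the model stands. The documents do not support that: at ρ = 0 nothing is lost. This part of the objection stands.

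A reader might also take baseline sVT/VF to be the only prognostic covariate in the plan. It is not. The stratification factors are also covariates, conditionally in SAP section 5.1 and outright in protocol section 7.2. Moreover, the outcome's own baseline is the natural first choice and, in simulation A, already removes more than half of the fitted dispersion (0.81 to 0.35). This stands too.

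It is equally tempting to turn the variance cut into a number of patients saved. That would rest on an assumed ρ and on the planned sample size, which an early-terminated trial did not reach. No such figure is given here.

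Three further points have some force:
- The share of patients with zero baseline sVT/VF is assumed, not documented.
- Devices in place for just over three months are allowed, so a full 12-month count does not exist for everyone. The fix has to deal with this.
- Neither document defines how nsVT is detected. Varying detection would weaken the covariate, but as a baseline value it would not bias the treatment comparison.

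The sample-size caveat in SAP section 5.1 is a fair reason to limit covariates. It weighs less against one continuous term than against a site factor over the eight sites in protocol section 3.1.

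**Conclusion.** The point holds as a suggestion for efficiency. Three facts are documented: entry is possible on nsVT alone, nsVT burden is used to mark risk, and it is absent from the primary model. The gain is conditional. Across both simulations the variance of the log rate ratio falls by about 0% at ρ = 0, 1–3% at 0.3, 4–8% at 0.5 and 8–19% at 0.7. These figures rest on log-normal patient effects, the assumed ρ, the assumed year-to-year stability and baseline rate of sVT/VF, and 191 per arm.

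A reader might go further and suspect a biased or invalid primary analysis. Nothing in the documents supports that. Treatment is randomised, the target rate ratio is the same with or without the covariate, and the rejection rate under the null barely moves. At an assumed 40 per arm, the gain of about 2 to 4 percentage points in power would not rescue an underpowered trial. The case for the change is that it costs almost nothing when nsVT is uninformative and helps modestly when it is not.

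**What to change.** In SAP section 5, state before unblinding that the primary negative binomial model also adjusts for log baseline nsVT burden, in addition to baseline sVT/VF. Define it as log[(nsVT count + 1) / look-back time], where look-back time is the part of the 12 months before randomisation during which the device was in place. Adding 1 covers patients who qualify under protocol section 4.1 through sustained episodes and have few or no nsVTs. If the sponsor prefers to omit the covariate, one line giving the reason would do.

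If unblinding has already occurred, keep the specified model as primary and report the nsVT-adjusted model as a labelled sensitivity analysis.

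The entry wording in protocol sections 4 and 4.1 and SAP section 3.2.1 should be reconciled, so that it is clear which episodes were counted.

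Cost: one sentence and one extra degree of freedom in a sample reduced by early termination. No new visits or measurements should be needed, because the count is required to check eligibility and the time since implantation is required to confirm more than three months of device therapy.
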